Smart Insulin Pens: A randomized, cross-over
prospective interventional pilot study assessing
the effect on glycemic control and diabetes
related burdens

NCT05036343

8/12/2021

General Study Information

Title of Project: Smart Insulin Pens: A randomized, cross-over prospective interventional pilot study assessing the effect on glycemic control and diabetes related burdens

Principle investigator: [name] Assistant Professor of Pediatrics, Division of Pediatric Endocrinology, Department of Pediatric and Adolescent Medicine.

Co-principle investigators: [name], DO., Fellow Division of Pediatric Endocrinology. [name], Professor of Pediatrics, Division of Pediatric Endocrinology, Department of Pediatric and Adolescent Medicine.

8/12/2021 version 9, 21-004938

Research Question and Aims

Project summary: Managing diabetes requires a burdensome number of tasks leading to fatigue, distress, and poor compliance, which often worsens during adolescence. Despite availability of diabetes technology including hybrid closed-loop pumps, over half of adolescents and emerging adults with T1D choose to stay on insulin injections rather than insulin pumps. Adolescents choosing injections need to administer insulin four to five times per day. Every injection requires actively calculating the insulin dose based upon the current blood sugar, insulin sensitivity, and estimated carbohydrates that will be consumed. Furthermore, for optimal glycemic control, these calculations and ratios need to be adjusted frequently. To meet these targets, teenagers need to reliably perform these cumbersome calculations three to five times per day. This is a struggle for many busy adolescents, resulting in poor control and more frequent hospital admissions for diabetic ketoacidosis. Thus, there is a critical need to reduce the burden of diabetes cares for people with T1D using injections and improve outcomes during adolescence and young adulthood.

The InPen® is a smartpen that has been FDA approved for children with diabetes age seven years and older. The pen has many features that decrease the burden of diabetes cares. **We plan to randomize 30 adolescents and emerging adults (13-21 years) to either: 1. InPen® with continuous glucose monitors (CGM) or 2. the standard of care with traditional insulin injections and CGM for 90 days and assess glycemic control and overall improvement in diabetes-related psychological burdens in both teens and parent.**

We also plan on having around 30 parents participate in this study as well due to their participation with some of the questionnaires. This will bring our total to 60 participants.

Specific aims:

Specific Aim 1: To determine whether the InPen® alters the glycemic control and variability in adolescents and emerging adults with type 1 diabetes.

Hypothesis: InPen® use improves glucose time in range, decreases mean glucose levels, and standard deviation assess by CGM. In addition, we expect to see an improvement in the number of missed insulin injection and hemoglobin A1c level.

Specific Aim 2: To determine if InPen® use alters the perceived burden of diabetes cares, diabetes distress scores, transition readiness scores, and parental experience of child illness scale (11-13).

8/12/2021 version 9, 21-004938

[figure not shown]
Hypothesis: InPen® use lessens the perceived burden of diabetes care, leading to decreased diabetes related distress in adolescent and improved parental experience in parent(s).

Study Design and Methods

Methods: *Describe in lay terms, completely detailing the research activities that will be conducted by Mayo Clinic staff under this protocol.*

Study Design:

We will perform a randomized, cross-over prospective interventional study. Half of the participants will be randomized to the InPen® and the other half will continue with their conventional insulin injection protocol. After 90 days, participants will switch to the second arm. Randomization will occur via block randomization. Teaching to use the InPen® will be done by [name], DO with supervision by [name], which can be done by a telemedicine visit if it does not align with clinic visit. Participants will be followed for three months with hemoglobin A1c at the beginning and the end of the study. Data from the CGM and InPen® will be analyzed including time in glucose goal range (70-180 mg/dL), glucose standard deviation, percentage of time that is spent high (>180-250 mg/dL), very high(> 250 mg/dL), low(54-70 mg/dL) and very low(<54 mg/dL), along with total daily insulin dose. Data on missed insulin doses will be assessed via data from the InPen®. For participants randomized to traditional injections we will ask them to record missed insulin doses weekly. Participants should still adjust insulin doses at home, like they do at baseline. If insulin adjustments are made while in one arm of the study they should still continue that dosing when they cross over. We will also assess quality of life and fatigue related to technology with surveys prior to start of the study and at the end. Specifically, we will assess diabetes distress, transition readiness, and parental experience of childhood illness scales [11-13]. We will also utilize the insulin delivery satisfaction survey to assess how they view their current regimen and then how they view the effects of the InPen in managing their type 1 diabetes [14].

Research Materials:

Blood Tests: no blood shall be drawn for research purposes

Downloadable data from CGM site and InPen® data from app.

Recruitment of Subjects: Participants will be recruited from Mayo Clinic Pediatric Diabetes Clinic. All participants will be fully informed about the study and they (or the parents of adolescents) will sign an informed consent/assent form before participating.

Participants of the study will have the option to consent via telemedicine visit if they are unable to come into the clinic. We will plan to arrange a telemedicine visit to go over the consent form, giving them 30 minutes to make sure they are still wanting to participate in the study. The consent form will be sent through their portal via a secure link to ensure that it goes to the correct patient. This will be sent out the day prior to the video visit to ensure the parent and child have time to look at it on their own. Due to this study taking place in individuals 13-21 years of age we will also make sure that the parent or legal guardian is also present. We will also make sure that the teenager/young adult is also present for the video visit.

We will also be consenting one parent of each child due to them needing to fill out a survey on how their child is managing their type 1 diabetes.

Potential Risks: Participants will need to learn to administer insulin with the new device. There is the potential that if an adolescent was previously not taking all their recommended insulin with traditional injections and they then receive all the recommended insulin that they could have a low blood sugar. However, this is not a risk beyond day to day life as person living with diabetes.

Confidentiality: All materials collected will be used for research purposes only and confidentiality will be assured by use of identification codes. Electronic data will be kept in a secure database, which is only accessible to the study investigators.

Protection: Participants will be monitored routinely in the clinic and will have access to medical advice 24/7.

Benefits: Participants will be receiving the InPen® and remuneration. They will also be helping advance further diabetes technology in this specific age group.

Subject Information

Target accrual is the proposed total number of subjects to be included in this study at Mayo Clinic. A “Subject” may include medical records, images, or specimens generated at Mayo Clinic and/or received from external sources.

Study Participants: We aim to recruit 30 patients with type 1 diabetes between the ages of 13-21 years, who will be using the InPen®. Type 1 diabetes will be defined as either a c peptide <1, one or more positive diabetes autoantibodies, or a clinical diagnosis with age of onset prior to puberty, based on chart review.

Patients are eligible if they currently receive insulin injections with a CGM. Given the nature of the study, patients will need to be able to read English and have access to a smart phone to participate. We will not exclude based on compliance or control.

Inclusion criteria:

- Individuals between the ages of 13 and 21 years.
- Patients with Type 1 diabetes for at least 6 months
- Defined as either a c peptide <1 , one or more positive diabetes autoantibodies, or a clinical diagnosis with age of onset prior to puberty
- Patients who currently receive insulin injections with a CGM.
- English speaking.
- Have access to a smart phone.
- Will also be recruiting parents/caregivers to fill out a study questionnaire during this study
- On an insulin to carbohydrate ratio

Exclusion criteria:

- Individuals less than 13
- Non-English speaking.
- No access to a smart phone.
- Intellectual disability that would impact their ability to utilize the technology
- Known pregnant women
- Taking chronic daily steroids (equivalent equal to or greater than 5mg of prednisone daily)

We will also recruit one parent for each child to participate in this study as well, estimate them to be less than 70s years of age. If a parent has two children who will be participating in this study then they will only have to consent one time. If we recruit no siblings we anticipate up to 30 adults, which will put are total study participants to 60.

For parent inclusion criteria they must have child with type 1 diabetes who is eligible for this study. We will want to make sure they can read English. They will be excluded from this study if they cannot read English and if their child does not have a diagnosis of type 1 diabetes.

Biospecimens

Collection of blood samples. When multiple groups are involved copy and paste the appropriate section below for example repeat section b when drawing blood from children and adults with cancer. Blood samples will be obtained as part participant's routine clinic visit and not part of the research visit.

- a. **From healthy, non-pregnant, adult subjects who weigh at least 110 pounds.** For a minimal risk application, the amount of blood drawn from these subjects may not exceed 550ml in an 8 week period and collection may not occur more frequently than 2 times per week.

Volume per blood draw: 0 ml

Frequency of blood draw (e.g. single draw, time(s) per week, per year, etc.) _____

b. **From other adults and children considering age, weight, and health of subject.** For a minimal risk application, the amount of blood drawn from these subjects may not exceed the lesser of 50 ml or 3 ml per kg in an 8 week period, and collection may not occur more frequently than 2 times per week.

Blood collected during this study will be limited to the glucose samples only (< 5 mL in total) and will not exceed 550 mL over a 12 week period (for adults) or 3 mL/kg body weight if body weight is <50 kg (for adolescents).

Prospective collection of biological specimens other than blood: _____ none _____

Review of medical records, images, specimens

Check all that apply (data includes medical records, images, specimens).

Only data that exists before the IRB submission date will be collected.

Date Range for Specimens and/or Review of Medical Records:

Examples: 01/01/1999 through 12/31/2015, or all records through mm/dd/yyyy.

Note: The Date Range must include the period for collection of baseline data, as well as follow-up data, if applicable.

The study involves data that exist at the time of IRB submission **and** data that will be generated after IRB submission. Include this activity in the Methods section.

Examples

- The study plans to conduct a retrospective chart review and ask subjects to complete a questionnaire.
- The study plans to include subjects previously diagnosed with a specific disease and add newly diagnosed subjects in the future.

The study will use data that have been collected under another IRB protocol. Include in the Methods section and enter the IRB number from which the research material will be obtained. *When appropriate, note when subjects have provided consent for future use of their data and/or specimens as described in this protocol.*

Enter one IRB number per line, add more lines as needed

Data Specimens Data & Specimens _____

Data Specimens Data & Specimens _____

Data Specimens Data & Specimens _____

Data Analysis

Power analyses may not be appropriate if this is a feasibility or pilot study, but end-point analysis plans are always appropriate even if only exploratory. Provide all information requested below, or provide justification if not including all of the information.

Power Statement:

Not needed

Data Analysis Plan:

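### As written, HbA1c and the Aim 2 scales are measured only at the start and the end, so no participant has an end-of-period value under both InPen and injections

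*Combined protocol and SAP*

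**What the plan says.** The Study Design section sets out a randomised cross-over with half the participants starting on each regimen: "After 90 days, participants will switch to the second arm". On follow-up and HbA1c it says: "Participants will be followed for three months with hemoglobin A1c at the beginning and the end of the study". On the questionnaires it says: "We will also assess quality of life and fatigue related to technology with surveys prior to start of the study and at the end". The sentence after that names diabetes distress, transition readiness and parental experience. The insulin delivery satisfaction survey is described separately and has no stated day.

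These outcomes belong to the stated aims. The Aim 1 hypothesis, after the CGM measures, adds: "In addition, we expect to see an improvement in the number of missed insulin injection and hemoglobin A1c level". Aim 2 names "diabetes distress scores, transition readiness scores, and parental experience of child illness scale". The Biospecimens section says blood comes from the "routine clinic visit and not part of the research visit" and gives no timing. The Data Analysis Plan promises summaries of paired differences and names the paired t-test only for glycemic curves. It does not say which two measurements make the pair for HbA1c or the scales.

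**The concern.** There are two separate problems. First, three months fits one 90-day period but not two, so the day meant by the end of the study is undefined. Second, and more serious, two measurement points are too few for a two-period cross-over on either reading. A within-person comparison of treatments needs a value at the end of each period, and one of them is never scheduled.

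Without that value, HbA1c and the Aim 2 scales lose the comparison that a cross-over is meant to provide. The only within-person pair left is end minus start. The plan does not say it would use that pair as the treatment contrast. If it did, a change due to study participation or season could be read as an InPen effect. A questionnaire that was not given at day 90 cannot be recovered later.

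**Working it through.** **1. Duration.** The plan's own figure is three months. Two periods × 90 days = 180 days, or 180/30.44 = 5.9 months. One period is 90/30.44 = 2.96 months. The stated figure therefore matches a single period and is not reproduced for the full cross-over.

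**2. What each schedule yields.**

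| Reading of the end | InPen-first sequence | Injections-first sequence | Participants with both |
|---|---|---|---|
| Day 90 | InPen only | Injections only | 0 of 30 |
| Day 180 | Injections only | InPen only | 0 of 30 |
| End of each period (days 90 and 180; not stated) | Both | Both | 30 of 30, before dropout |

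**3. What the available contrasts estimate.** Let τ be the InPen effect, λ the part of it carried into a following injection period, and trend₉₀ and trend₁₈₀ the change over time common to everyone. With equal sequences:

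- End minus start, day 90: the sequences average τ + trend₉₀ and trend₉₀, so the pooled value is τ/2 + trend₉₀.
- End minus start, day 180: the sequences average λ + trend₁₈₀ and τ + trend₁₈₀, so the pooled value is (τ + λ)/2 + trend₁₈₀.
- Between sequences, day 90: τ.
- Between sequences, day 180: τ − λ.
- Cross-over contrast adjusted for period: the average of τ and τ − λ, which is τ − λ/2.

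End minus start thus carries half the InPen effect (absent carryover at day 180) plus the whole time trend. Carryover is plausible because the protocol says: "If insulin adjustments are made while in one arm of the study they should still continue that dosing when they cross over". Its size is unknown. If λ were half of τ (an assumption), the day-180 between-sequence estimate would recover 50% of the effect and the cross-over contrast 75%. A day-90 between-sequence estimate would have no carryover bias.

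**4. Precision.** From the protocol: N = 30, half to each sequence (15 and 15), two-sided alpha 0.05. Assumed: equal variances, the same correlation ρ between any two occasions (0.5 to 0.8), 80% power, no dropout. Standard errors are in SD units:

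- Cross-over: √(2(1−ρ)/30)
- Between sequences, baseline-adjusted (ANCOVA): √((2/15)(1−ρ²))
- Between sequences, change score: √(4(1−ρ)/15)

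The variance ratio to the cross-over is 2(1+ρ) for ANCOVA and 4 for the change score at any ρ. The N needed to match 30 cross-over participants is 30 times that ratio. Detectable differences use the noncentral t distribution with 28 df (cross-over) and 27 df (ANCOVA).

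| ρ | SE cross-over | SE ANCOVA | SE change | Variance ratio, ANCOVA | N to match, ANCOVA | Detectable, cross-over (SD) | Detectable, ANCOVA (SD) |
|---|---|---|---|---|---|---|---|
| 0.5 | 0.183 | 0.316 | 0.365 | 3.0 | 90 | 0.53 | 0.92 |
| 0.6 | 0.163 | 0.292 | 0.327 | 3.2 | 96 | 0.47 | 0.85 |
| 0.7 | 0.141 | 0.261 | 0.283 | 3.4 | 102 | 0.41 | 0.76 |
| 0.8 | 0.115 | 0.219 | 0.231 | 3.6 | 108 | 0.34 | 0.64 |

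For the change score the matching N is 30 × 4 = 120.

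**The case against.** The strongest reply is that the authors meant the beginning and end of each period. Three months equals one period, and the project summary also speaks of 90 days, so the sentence may describe one arm. That is possible, and the remedy would then be wording alone. But the text says the end of the study, and staff who followed it would give no survey at day 90. The copy reviewed also lacks one figure, placed before the Study Design section and of unknown content. If it is a schema showing a day-90 assessment, the text still has to be brought into line with it.

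Baseline is taken on injections, so participants whose end value is on InPen do have one value under each regimen. That baseline precedes the study, however, and is confounded with time. The other sequence either has no InPen value (day 180) or has no second-period value to set beside it (day 90).

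Routine visits may happen to supply an HbA1c near day 90, so for HbA1c the loss is not certain. None is scheduled, and a routine visit does not supply the questionnaires.

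The trial is a pilot with no power target, so the precision figures are illustrative. Carryover also affects the CGM outcomes and is not removed by the fix. Both points are fair. Neither changes the count of 0 of 30, which needs no assumption about variance or carryover.

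**Conclusion.** The concern holds: the schedule is wrong as written. Under either reading of the end of the study, 0 of 30 participants have end-of-period values under both regimens for HbA1c or the three named scales. Aim 2 suffers most, because no later data source can stand in for a missed questionnaire. Aim 1 is only partly touched: its leading CGM outcomes are unaffected, and HbA1c is an additional outcome there.

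The loss of precision (3.0 to 3.6 times the variance with baseline adjustment, 4 times with change scores) rests on the assumed correlation of 0.5 to 0.8, equal variances and 15 per sequence. The carryover percentages rest on an assumed λ.

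**What to change.** - Reconcile the three-month statement with the two 90-day periods, and state the total duration.
- Give all participant and parent surveys at baseline, at day 90 before the switch, and at day 180. Include the satisfaction survey, which also needs stated days.
- Take HbA1c from routine clinic visits within a stated window around days 90 and 180. Where no visit falls in the window, report the value as missing and give the number missing by period. Keep CGM mean glucose as a separate outcome, not a substitute.
- Define the contrast for these outcomes as the end-of-InPen-period value minus the end-of-injection-period value, with period in the model, and state carryover as a limitation.

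The cost is protocol wording and one extra round of questionnaires already in use. No research blood draw is added. Some HbA1c values will be missing, since they come only from routine visits. The protocol allows for people who cannot attend in person, though it says so about consent: "Participants of the study will have the option to consent via telemedicine visit if they are unable to come into the clinic".

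### The paired t-test does not separate period effects and carryover from the InPen effect; a treatment-period-sequence model and a stated equal-carryover assumption are a cheap improvement (minor)

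*Combined protocol and SAP*

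**What the plan says.** All references are to the combined protocol and SAP.

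- **Study Design.** Half the participants start on InPen and half on their usual injections. "After 90 days, participants will switch to the second arm". No washout is described. On dosing: "Participants should still adjust insulin doses at home, like they do at baseline", and then "If insulin adjustments are made while in one arm of the study they should still continue that dosing when they cross over". On allocation: "Randomization will occur via block randomization". The outcomes are CGM measures, "along with total daily insulin dose".
- **Project summary (Research Question and Aims).** 30 participants are randomized to InPen with CGM or to "the standard of care with traditional insulin injections and CGM for 90 days and assess glycemic control". It also says that "for optimal glycemic control, these calculations and ratios need to be adjusted frequently".
- **Data Analysis Plan.** It gives descriptive summaries of measurements and paired differences, two-sided tests at 0.05, and paired t-tests on glucose curves within participants, with a transformation or nonparametric test if needed. It names no period term, sequence term or between-group comparison, and it does not define the pair.
- **Inclusion criteria.** "Patients who currently receive insulin injections with a CGM".

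**The concern.** The design section creates a route from period 1 into period 2, because a dose change made in one arm stays in force in the other. The analysis section has nothing that deals with it. A pooled paired mean estimates the InPen effect cleanly only if the two arms leave equal carryover and the two sequences contribute equal numbers. The plan states neither condition. Block randomization balances who enters each sequence, not who completes.

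At stake is the glycemic contrast of Aim 1. Completer imbalance lets period effects and even equal carryover into the estimate. Unequal carryover shifts it whatever the numbers. Even with perfect balance, an ordinary period effect inflates the error term of a paired t-test that ignores period.

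The point is limited to outcomes measured in both periods: the CGM measures and total daily insulin dose. HbA1c and the surveys are described only at the beginning and end of the study, so on that text they give no period-by-period contrast.

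**Working it through.** **Inputs from the documents:** 30 participants, half per sequence (15/15), 90-day periods, direct switch, two-sided alpha 0.05. The plan gives no figure to reproduce; its power statement says none is needed.

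**Inputs assumed for illustration:** true effect τ = 5 time-in-range points; carryover cA (after InPen) and cB (after injections); period effect π (period 2 minus period 1); SD of the within-participant difference 10; various completer counts. nA and nB are completers in the InPen-first and injections-first sequences, and N = nA + nB.

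**Model.** The expected InPen-minus-injections difference is:
- InPen-first: τ − cA − π
- injections-first: τ + cB + π

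Pooled paired mean = τ + (nB·cB − nA·cA)/N + π(nB − nA)/N.
Sequences weighted equally = τ + (cB − cA)/2, where π cancels.

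**1. Unequal completers, equal carryover (cA = cB = 2.5).** Half-widths are 95%, with no period effect. Paired: t(N−1)·10/√N. Equally weighted: t(N−2)·(10/2)·√(1/nA + 1/nB).

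| Completers | Pooled mean | Share of π added | Equally weighted | Half-width, paired | Half-width, equally weighted |
|---|---|---|---|---|---|
| 15/15 | 5.0 | 0 | 5.0 | 3.73 | 3.74 |
| 15/13 | 5 − 2.5×2/28 = 4.8 | −0.07 | 5.0 | 3.88 | 3.89 |
| 15/12 | 5 − 2.5×3/27 = 4.7 | −0.11 | 5.0 | 3.96 | 3.99 |
| 15/10 | 5 − 2.5×5/25 = 4.5 | −0.20 | 5.0 | 4.13 | 4.22 |

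At 15/10, a period effect of +2 or −2 gives 4.1 or 4.9. If the losses fall in the InPen-first sequence instead, the signs reverse: 10/15 gives 5 + 2.5×5/25 = 5.5.

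**2. Balanced completers (15/15).** The estimate is unaffected by π or by equal carryover, but the paired t-test's error term is not. Let δ be the period effect plus the equal carryover. The expected variance of the pooled differences is 100 + δ²×30/29.
- δ = 2.5: √106.5 = 10.32; half-width 2.045×10.32/√30 ≈ 3.85
- δ = 5: √125.9 = 11.22; half-width 2.045×11.22/√30 ≈ 4.19

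With period in the model the half-width stays at 3.74.

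**3. Unequal carryover.** The bias is (cB − cA)/2, with or without period in the model. For cA = 2.5 and cB = 0, constant through all of period 2, it is −1.25 (estimate 3.75). If carryover starts at 2.5 and decays with half-life h, its 90-day average is 2.5×(1 − e^(−90k))/(90k), where k = ln 2/h.
- h = 7 days: average 0.28, bias 0.14 in size
- h = 14 days: average 0.55, bias 0.28
- h = 30 days: average 1.05, bias 0.53

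**4. Period-1 comparison, 15 v 15.** This is free of carryover. Take ANCOVA on the pre-randomization value, with equal correlation ρ among baseline and both periods and outcome SD 10/√(2(1−ρ)). Simulation (20,000 trials) gave half-widths of 6.55 (ρ = 0.5) and 7.18 (ρ = 0.8). A direct check agrees closely: 2.052×8.66×√(2/15) = 6.49 and 2.052×9.49×√(2/15) = 7.11, before the small allowance for chance baseline imbalance. In the same simulations with cA = 2.5 and cB = 0, a 5% test of the gap between the period-1 and cross-over estimates was significant in 7.4% or 6.9% of trials, against 5% by chance.

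**The case against.** The strongest reply is that nothing is shown to be wrong. The documents report no carryover, and doses are meant to be readjusted continually, so a retained dose may soon be superseded. A shift lasting all 90 days is therefore an upper-end illustration. With decay, the bias is a fraction of a point against a CI of about ±3.7. This stands, and it is the main reason the point is minor.

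A second reply is that the contrast is inferred, because the plan never says what is paired. That also stands. The consequences above follow from the natural cross-over reading, and defining the contrast belongs in the same repair.

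A third reply is that the remedy adds little: equal weighting does not move the estimate at 15/15, and the period-1 interval is too wide to expose a bias of 1 to 2 points. This is partly right. The model still protects against unequal completion and keeps a period effect out of the error term, at almost no cost.

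The pilot label answers less than it seems to. The Data Analysis section's own instructions excuse a power calculation in a pilot but still expect an endpoint analysis plan, and this plan commits to tests at 0.05.

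A reader might also infer that retained dosing inflates the InPen effect. The documents do not support that. Inflation would need injections to leave the larger benefit, and no text points that way. If InPen benefit persists, as the trial's hypothesis would suggest, the bias is toward no effect.

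**Conclusion.** The point holds as a cheap improvement, severity minor. What is certain is textual: dose changes persist across a direct switch, the only named comparison is a paired test without period or sequence, and the equal-carryover assumption is not stated. The size is not established.

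Under the assumptions shown, completer imbalance from 15/13 to 15/10 moves an effect of 5 by about 0.2 to 0.5 points, plus 7% to 20% of any period effect. At 15/15 the cost is only a wider interval. Unequal carryover contributes at most 1.25 points in the constant 2.5-point case and about 0.14 to 0.53 with decay. Its direction is unknown: dilution fits the trial's hypothesis, while inflation cannot be excluded but has no specific support.

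Two stronger readings should be resisted. The documents do not show that the planned estimate is biased, only that it rests on unstated conditions. The lack of a planned carryover-free estimate also does not mean the period-1 comparison should replace the cross-over one; at this sample size it is too imprecise.

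**What to change.** Changes to the Data Analysis Plan only; no change to dosing, schedule or sample size.

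1. Define the contrast as InPen minus injections. Replace the paired t-test with a cross-over model containing treatment, period and sequence, which among completers is equivalent to weighting the two sequences equally. Show the difference by sequence descriptively only, because a gap between sequences mixes carryover with period effects.
2. Always report the period-1 InPen-first versus injections-first estimate, adjusted for pre-randomization CGM over a fixed window, with its 95% CI. Label it a secondary sensitivity estimate. Do not make it conditional on a carryover test or use it as one.
3. Add a sentence such as: *The cross-over estimate assumes equal carryover from the two arms; unequal carryover could bias it in either direction.*

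**Cost.** Wording, plus a download of pre-randomization CGM data, which participants should already generate because CGM use is an entry criterion. With no period effect, the CI half-width rises from 3.73 to 3.74 at 15/15, from 3.96 to 3.99 at 15/12 and from 4.13 to 4.22 at 15/10 (assumed difference SD 10). The period-1 interval, about ±6.5 to 7.2, cannot detect or rule out a bias of 1 to 2 points, and the report should say so.

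### HbA1c is an Aim 1 outcome, but no end-of-period-1 reading is clearly planned and nothing ties a routine-visit draw to the 90-day switch, so such a reading could mix both treatments

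*Combined protocol and SAP*

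**What the plan says.** - **Outcome.** Under Specific Aim 1 the hypothesis lists the CGM measures first and then adds: "we expect to see an improvement in the number of missed insulin injection and hemoglobin A1c level".
- **Schedule.** The only HbA1c schedule is in Study Design: "Participants will be followed for three months with hemoglobin A1c at the beginning and the end of the study".
- **Switch.** The same section has participants change arms once 90 days have passed. It states no washout, and no visit or sample that must come before the change.
- **Source of blood.** Research Materials says "no blood shall be drawn for research purposes". Biospecimens says samples come from the "routine clinic visit and not part of the research visit".
- **Type of blood.** Biospecimens, item b, says: "Blood collected during this study will be limited to the glucose samples only". HbA1c is not mentioned there.
- **Visit alignment.** The only remark is about InPen teaching, "which can be done by a telemedicine visit if it does not align with clinic visit".
- **Analysis.** The Data Analysis Plan calls for summaries of paired differences and within-subject paired t-tests, two-sided at 0.05. It names neither HbA1c nor any rule for the timing of a reading. The Power Statement says that none is needed.

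**The concern.** Two gaps combine.

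First, a within-participant comparison of HbA1c between arms needs a value that belongs to each arm. A schedule with one reading at the start and one at the end of the study does not supply that.

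Second, treatment changes by the calendar while the blood sample follows the routine clinic diary, and no rule joins the two. HbA1c reflects glucose over preceding weeks. A value meant to represent the first period but drawn after the switch gives part of its weight to the second treatment. A site could follow the protocol fully and still record such a value.

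Mixing pulls the estimated InPen effect on HbA1c towards zero. Pairing cannot undo this, because the error is in the reading and not in between-participant variation. A null HbA1c result would then be hard to interpret.

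**Working it through.** The plan gives no effect size, SD, power or computed sample size, so there is no figure of its own to reproduce.

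**Step 1: what the schedule can support.** The mention of three months allows more than one reading:

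| Meaning of the end of the study | HbA1c values available | Paired InPen v conventional contrast |
|---|---|---|
| End of the second period (day 180 if it also lasts 90 days, an assumption) | day 0 and day 180 | none: no first-period value |
| Three months after the start | day 0 and about day 90 | none: no second-period value; the end reading falls at the switch |
| Start and end of each period | day 0, about day 90, day 180 | possible, but the day-90 draw is not tied to the switch |

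Under the first reading, half the participants end on each treatment. With the weightings below, the pooled start-to-end change carries only 0.49-0.50 of the InPen effect. What remains is a between-sequence comparison of about 15 v 15.

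**Step 2: effect of a late first-period draw.** Assume a constant InPen effect, conventional injections before the study, and a second-period reading on day 180. Let F(t) be the share of an HbA1c value that reflects the last t days, and d the days from the switch to the first-period draw. The share of the true contrast retained is:

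- InPen first: [F(90+d) − F(d)] − [F(180) − F(90)]
- Conventional first: F(90) − F(d)
- Trial: the average of the two

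The documents give no F, so five were assumed: weight declining linearly to zero over 120 days, F(t) = 1 − (1 − t/120)²; 50/25/25% for days 0-30, 30-60 and 60-120; uniform over 90 days; uniform over 120 days; exponential with a 30-day half-life.

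Worked case, linear over 120 days: F(30) = 1 − 0.75² = 0.4375; F(90) = 1 − 0.25² = 0.9375; F(120) = F(180) = 1.

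- d = 0: (0.9375 − 0.0625 + 0.9375)/2 = 0.906
- d = 30: InPen first (1 − 0.4375) − 0.0625 = 0.500; conventional first 0.9375 − 0.4375 = 0.500; average 0.500

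| Weighting | d = 0 | 14 days late | 30 days late | 60 days late | Half of the d = 0 contrast lost at |
|---|---|---|---|---|---|
| Linear, 120 days | 0.906 | 0.709 | 0.500 | 0.188 | 34 days |
| 50/25/25% | 0.812 | 0.608 | 0.375 | 0.125 | 28 days |
| Uniform, 120 days | 0.625 | 0.567 | 0.500 | 0.250 | 53 days |
| Uniform, 90 days | 1.000 | 0.844 | 0.667 | 0.333 | 45 days |
| Exponential | 0.820 | 0.561 | 0.352 | 0.117 | 25 days |

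**Step 3: illustrative power.** For a paired t-test with n = 30, two-sided alpha 0.05 and an assumed full standardised paired effect of 0.5, power is 0.75 without mixing. It is 0.38-0.75 at d = 0, 0.15-0.42 at 30 days late and 0.06-0.14 at 60 days late.

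**Step 4: an early draw.** If the first-period reading is 14 days early, the InPen-first term becomes F(76) − [F(180) − F(90)] and the conventional-first term becomes F(90). The averages, in table order, are 0.870, 0.783, 0.567, 0.922 and 0.796. Early is better than equally late under four weightings and equal under uniform-120. An early draw loses exposure time, but it never contains the other treatment.

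**The case against.** The strongest reply is that the harmful reading is not in the plan. If the end of the study means the end of the second period, neither scheduled HbA1c lies near the switch, and there is no first-period value to contaminate. That is a fair account of the text. It means the missing reading is the more basic gap, and timing becomes a problem once the reading is added or if the schedule is meant per period. It does not rescue the HbA1c comparison.

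A reader might infer three stronger points that the documents do not support:

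- **That the protocol expects clinic visits to miss the study days.** The alignment remark is conditional and concerns device teaching. It allows for misalignment there and says nothing about blood draws. Recruitment is from one clinic with routine monitoring, and no visit-timing data are given.
- **That a late draw generally destroys the contrast.** A between-group comparison at the end of period 1, with weight declining linearly over 90 to 120 days, would retain 39-52% at 15 days late and −11% to 13% at 30 days. But the plan specifies paired comparisons. With those same two weightings the paired contrast is about 69% at 15 days and 44-50% at 30 days.
- **That HbA1c cannot be obtained at all.** Drawing no blood for research is compatible with using a value from routine care. The glucose-only statement is a wording conflict and not evidence about timing.

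It is also fair to say that HbA1c comes after the CGM measures in Aim 1 and that this is a pilot with no power claim. Both limit the weight of the point.

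**Conclusion.** The concern holds in a limited form. For an outcome named in the Aim 1 hypothesis, the plan does not clearly provide an end-of-period-1 reading, and nothing stops such a reading from being drawn after the switch.

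The size depends on assumptions about how HbA1c weights past glucose and on a delay that the documents do not quantify. A delay of two weeks leaves 56-84% of the paired contrast and a delay of 30 days leaves 35-67%, against 63-100% for a switch-day draw. Half or more of the on-time contrast is lost only at about 25 to 53 days or later. The calculation also assumes a constant InPen effect from the first day of use.

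Time in range, mean glucose and glucose SD come from CGM and are not affected. The plan should be changed, but Aim 1 as a whole is not undermined.

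**What to change.** 1. In Study Design, name an HbA1c at the end of each 90-day period, taken at a routine clinic visit. Schedule the switch at or after that visit, within a stated window around day 90.
2. Record each draw date relative to the switch.
3. In the Data Analysis Plan, state that the HbA1c treatment comparison uses only readings from the last 14 days of a period, or from the switch day before the next arm starts. Treat other readings as missing and rely on CGM mean glucose for that period. The switch-day draw should be the target: step 4 of the working shows that an early draw also gives up some contrast.
4. Reconcile the three-month follow-up with two 90-day periods, and the glucose-only statement in Biospecimens item b with the HbA1c outcome.

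**Cost.** The changes are to wording and should need no research blood draws or added research visits, provided that routine visits can be booked near the end of each period. Period length will vary somewhat between participants. An unknown number of readings will fall outside the window and be lost. With no visit-timing data, that number cannot be assumed to be small among 30 participants.
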